Mindfulness and Cognitive Behavioral Therapy for Sleep in Cancer

NCT04736056

Document Date: May 10, 2023

Purpose of the Study

In this study, we will develop and pilot test the MBTI+ protocol for one-on-one, home-based delivery to hematologic cancer patients (i.e., acute myeloid leukemia, acute lymphoblastic leukemia, Non-Hodgkin's lymphoma, multiple myeloma, myelodysplastic syndrome) reporting insomnia, fatigue, pain, and distress after any cycle of inpatient chemotherapy treatment.

Study Phase I (months 0-6) will use patient (3 patient focus groups, approx. 4 patients in each focus group) and provider (1 provider focus groups, approx. 6 providers in focus groups) focus groups to adapt MBTI+ for individual treatment and improved symptom management. Intervention timing, scaling, and content will be further refined through iterative patient testing (months 6-12; N=5). The specific aims and hypotheses are:

Aim 1: To develop and refine the MBTI+ protocol for individual, home-based delivery to hematologic cancer patients reporting insomnia, fatigue, pain, and distress following discharge from any cycle of inpatient chemotherapy treatment. Patient (3 patient focus groups, approx. 4 patients in each focus group) and provider (1 provider focus groups, approx. 6 providers in focus groups) focus groups, along with theory and expert opinion, will inform intervention adaptation. The MBTI+ protocol will be refined through an iterative patient testing process (N=5). Hypothesis: These activities will result in a manualized MBTI+ protocol including patient materials (i.e., study workbook, study folder) and a structured therapist manual (e.g., timing, scaling, content) that can be used to standardize the intervention.

Study Phase II (months 12-36) will be a single-arm pilot (N=30). Patient-reported outcomes will be assessed at baseline, post-treatment, and 1-month follow-up. The specific aims and hypotheses are:

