Initial feasibility and acceptability of MBTI+ will be assessed with 5 hematologic cancer participants recruited for user testing. Participants will be asked to complete six, 60- to 75-minute intervention sessions with a study therapist. Interventions sessions will be done in-person or via a videoconferencing program (i.e., Zoom), depending on feedback given during focus groups. Participants will be asked to complete daily sleep diaries before each session, and at the beginning of each session participants will be asked several questions about any recent cancer treatments, use of sleep and/or pain medication, and coping skill use. The study sessions will be audio recorded by the therapist using the program Voice Recorder. A subset of these recordings will be reviewed by the study PI and research team to improve the intervention and ensure therapist fidelity to the intervention. Sessions recordings will be stored on a secured drive behind the Duke firewall. These recordings will be destroyed upon study completion. There are three assessments we will ask all participants to complete. They each take about 30-40 minutes and include questions about the participant and their background, their cancer symptoms (e.g., insomnia, fatigue, pain), and their emotions (e.g., symptoms of depression, anxiety, hyperarousal). Participants will also be asked to give feedback on the sessions and intervention content; feedback will be used to make the intervention better for other patients who receive it in the future. The first survey is completed at the start of the study. The second survey is about 7 weeks later and the final survey is about 11 weeks after the start of the study. Study staff will be blinded to outcome assessments, as these will be completed online (i.e., via Redcap). Participants will receive \$40 for completing each of the three study assessments. Total compensation may be up to \$120.

Selection of Subjects

Eligibility criteria for patients included in Phase I and Phase II include:

- 1) an initial or recurrent/relapse diagnosis of acute myeloid leukemia, acute lymphoblastic leukemia, Non-Hodgkin's lymphoma, multiple myeloma, myelodysplastic syndrome
- 2) within 8 weeks of discharge home after inpatient chemotherapy or CAR-T therapy
- 3) score of 8 or greater on the Insomnia Severity Index (ISI);

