
Treatment Feasibility and Acceptability. Feasibility. Feasibility will be assessed by session attendance ($\geq 80\%$) and attrition ($\leq 20\%$). Acceptability. Satisfaction will be measured post-intervention using the Client Satisfaction Questionnaire 8-item version. The scale includes eight items assessing the participant's level of satisfaction with treatment, with response options ranging from 1 (quite dissatisfied) to 4 (very satisfied). Acceptability will be demonstrated by 80% of participants reporting intervention satisfaction on the Client Satisfaction Questionnaire. Engagement in the intervention will be assessed at the beginning of sessions 3 and 6, and post-intervention follow-up. The participant will be asked about his or her coping skills practice and completion of homework assignments from the previous time point. These data will be recorded by the study therapist in RedCap.

Demographics and Medical Information: At baseline, participants will report their education, household income, employment status, and history of comorbidities (e.g., hypertension, heart disease). At each assessment, participants will also be asked about their cancer treatments in the last 7 days (chemotherapy, radiation, surgery, hormone therapy, vaccine, pill anti-cancer drug) and how many days in the last 7 they have taken any type of pain and/or sleep medication.

Risk/Benefit Assessment

Risks:

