There are numerous potential benefits of the proposed research. Providers and hematologic cancer patients who participate in the focus group may learn about skills that can help reduce nighttime sleep disturbances and daytime symptoms of fatigue, pain, and psychological stress. Participants who participate in user testing or the single-arm pilot will receive a mindfulness and cognitive-behavioral intervention at no cost. As demonstrated in prior mindfulness and behavioral symptom management studies, the proposed intervention may lead to improvements in patients' nighttime sleep and daytime symptoms of fatigue, pain, and distress. Furthermore, information learned from this study may benefit other patients with cancer in the future. Lessons learned will provide a foundation for subsequent larger, methodologically rigorous, randomized efficacy trials of adapted MBTI. This research program could also serve an heuristic purpose in encouraging researchers to extend adapted MBTI to other cancer and chronic illness populations reporting insomnia and daytime fatigue, pain, and distress. Future work might examine the effects of adapted MBTI on neuroendocrine and immune markers that are linked to sleep and have implications for cancer progression.

Data Analysis & Statistical Considerations

Sample size and statistical power: Part 1 of Phase I will include three focus groups comprised of 4 patients and one provider focus group comprised of 6 medical providers. User testing (Part 2, Phase I) will involve 5 patients. This sample size is based on our prior work using focus groups in the hematology-oncology setting.²⁷ Research suggests that 2-3 focus groups are sufficient to reveal 80% of themes.⁷⁰ If the intervention content is not significantly altered during user testing, these participants will be combined with those from Phase II for an intent-to-treat sample of 35 participants.

Analytic Plan

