Aim 1: Focus groups with hematologic cancer patients and their providers will be transcribed verbatim and analyzed using Atlas.ti. An initial coding scheme will be developed based on a review of literature, our research goals, and prior work, as well as themes that emerged during focus groups. The codes will be applied to the transcripts in Atlas.ti. Two independent individuals, including [name], will code each transcript to ensure similar understanding of the codes and consistency in judgement.⁷² As part of the training plan, [name] will complete several workshops on analyzing qualitative data. Additionally, the study sponsors and the mentoring team have extensive experience with qualitative analyses, and access to a shared resource of qualitative experts to assist with these analyses and any challenges that may arise.

Aim 2: Feasibility (i.e., $\geq 80\%$ of sessions completed; attrition $\leq 20\%$) and acceptability (i.e., 80% of participants reporting intervention satisfaction on the Client Satisfaction Questionnaire, participant completion of homework assignments) data will be examined using descriptive statistics (mean, median, standard deviation, percent etc.). Paired sample t-tests will be run to quantify the degree of change over time for all primary and secondary outcomes. Effect sizes will be computed using Cohen's d. Unconditional latent growth models will be used to assess main time effects across baseline, post-treatment, and 1-month follow-up. Time will be coded as the number of months since the baseline assessment. Determination of linear versus quadratic change will be made by comparing the relative fit of the two models using the Bayesian Information Criterion, as recommended. Control variables and their interactions with time will be included in the conditional models. Analyses will be conducted on an intent-to-treat basis to make use of all available data (N=35).

Data & Safety Monitoring

The proposed study carries minimal risk. The protocol does not use an investigational drug, procedure, or device. Data obtained from participants will include information from medical chart review, patient and provider focus groups, and self-report inventories. The study team considers the management of participant information and data as a key priority. Best practices for confidentiality and data management will be observed.

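### Feasibility and acceptability are judged by point estimates against 80%/20% cut-offs with no confidence interval, and acceptability is called demonstrated at a sample figure of 80%

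*Combined protocol and SAP*

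**What the plan says.** Hypothesis 1 of Aim 2 (Purpose of the Study) sets three criteria: at least 80% of sessions completed, at most 20% attrition, and 80% of participants satisfied. The same cut-offs recur in Design & Procedures, in Treatment Feasibility and Acceptability, and in the Analytic Plan, which gives the acceptability criterion as "80% of participants reporting intervention satisfaction on the Client Satisfaction Questionnaire".

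The wording differs between criteria. Treatment Feasibility and Acceptability says that feasibility is to be assessed by attendance and attrition, but for satisfaction it says: "Acceptability will be demonstrated by 80% of participants reporting intervention satisfaction on the Client Satisfaction Questionnaire". That section also places the satisfaction questionnaire after the intervention.

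On method, the Analytic Plan for Aim 2 says that these "data will be examined using descriptive statistics (mean, median, standard deviation, percent etc". No interval, unacceptable rate or error rate is given for any of the three criteria.

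On size, Phase II "will be a single-arm pilot (N=30"). The sample-size paragraph adds that "User testing (Part 2, Phase I) will involve 5 patients" and that, if content is not significantly altered, "these participants will be combined with those from Phase II for an intent-to-treat sample of 35 participants". That paragraph states no precision for 30 or 35 patients; its supporting argument concerns focus groups and theme saturation.

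**The concern.** A sample percentage from 30 to 35 patients is an imprecise estimate of the rate that a later trial would meet. If 24 of 30 patients report satisfaction, the plan as written lets the report say that acceptability has been demonstrated, with nothing beside the figure to show how low the true rate could be. The attrition criterion has the same problem in mirror image: 6 losses among 30 would be reported as meeting the limit, with no indication of how much higher true attrition might be. What is at stake is the strength of the Hypothesis 1 conclusion, which readers planning further work will take from the report.

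**Working it through.** The documents give no power, precision or error rate for these criteria, so there is no such figure to reproduce. The one stated total, 30 + 5 = 35, is correct.

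**Inputs.** Cut-offs of 80% and 20% (Aim 2; Treatment Feasibility and Acceptability). n = 30 (Purpose of the Study) or 35 (Sample size and statistical power). Six sessions per patient (Phase I: User Testing and Phase II: Single Arm Pilot: "Participants will be asked to complete six, 60- to 75-minute intervention sessions with a study therapist"). Pass marks: 0.80 × 30 = 24 and 0.80 × 35 = 28 satisfied; 0.20 × 30 = 6 and 0.20 × 35 = 7 lost. True rates and the within-patient correlation are assumptions, shown as ranges.

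**Step 1: precision at the cut-off.** Exact (Clopper-Pearson) 95% limits for x of n: lower = 2.5% quantile of Beta(x, n − x + 1); upper = 97.5% quantile of Beta(x + 1, n − x).

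| Criterion | Result at cut-off | Exact 95% CI |
|---|---|---|
| Satisfaction | 24/30 | 61.4% to 92.3% |
| Satisfaction | 28/35 | 63.1% to 91.6% |
| Attrition | 6/30 | 7.7% to 38.6% |
| Attrition | 7/35 | 8.4% to 36.9% |

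The interval spans 92.3 − 61.4 = 30.9 points at n = 30 and 91.6 − 63.1 = 28.5 points at n = 35. For the lower limit for satisfaction to reach 70%, at least 27/30 or 31/35 must be satisfied; to reach 80%, at least 29/30 or 33/35.

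**Step 2: how well the rule separates good from poor rates.** P(pass) = P(X ≥ r), with X binomial(n, p), r = 24 for n = 30 and r = 28 for n = 35. The attrition rule gives the same figures with true attrition 1 − p.

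| True rate p | n = 30 | n = 35 |
|---|---|---|
| 60% | 0.017 | 0.010 |
| 65% | 0.059 | 0.042 |
| 70% | 0.160 | 0.133 |
| 75% | 0.348 | 0.322 |
| 80% | 0.607 | 0.599 |
| 85% | 0.847 | 0.856 |
| 90% | 0.974 | 0.980 |

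Between 75% and 85% the outcome is uncertain. At 65% or below, and at 90% or above, the rule gives the right answer at least 94% of the time (1 − 0.059 = 0.941).

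**Step 3: the satisfaction denominator.** If 20% drop out and do not answer, 24 of 30 or 28 of 35 respondents remain. The pass marks become 20/24 (0.80 × 24 = 19.2, rounded up) and 23/28 (0.80 × 28 = 22.4, rounded up). The exact 95% CI at 20/24 is 62.6% to 95.3%, a span of 32.7 points.

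**Step 4: session completion.** If pooled, the denominator is 6 × 30 = 180 or 6 × 35 = 210 sessions, clustered within patients. Half-width at 80% = 1.96 × √(0.80 × 0.20 × [1 + 5 × ICC] / sessions). With ICC = 0 this is 5.8 points (180 sessions) or 5.4 points (210). With ICC = 1 it is 14.3 or 13.3 points. Unless sessions within a patient are fully correlated, this criterion is more precise than one based on 30 to 35 patients.

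**The case against.** The strongest reply is that this is a single-arm pilot. Descriptive benchmarks are an acceptable choice there, no hypothesis test is needed, the list of statistics is left open, and a reader can compute an exact interval from reported counts. That stands as far as it goes: the point is about reporting and wording, not a call for a test or a larger sample. It does not excuse calling acceptability demonstrated at a sample figure of 80%. An open-ended list does not exclude an interval, but it does not commit the team to one either.

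Four stronger readings are tempting, and the documents do not support them.

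- A reader might infer that the criteria pass or fail mostly by chance. Step 2 shows otherwise, except close to the cut-off.
- A reader might treat the roughly 40% chance of failing at a true rate of exactly 80% as a small-sample defect. Any cut-off placed at the true rate behaves in much this way: the pass probability is 0.56 at n = 100 and 0.51 at n = 3000.
- A reader might infer that these benchmarks decide whether a randomized trial follows. No section makes them a stop/go rule. Background & Significance ties support for such a trial to observed reductions in insomnia symptoms, and the Benefits section speaks only of lessons learned.
- A reader might extend the demonstration wording to feasibility, but it is used only for acceptability.

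It is also fair to say that an interval does not settle what counts as satisfied: the plan gives no questionnaire score for this. That gap is separate and would remain.

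**Conclusion.** The point holds as a matter of precision and wording. Following the plan as written, acceptability could be declared demonstrated on data that do not exclude true satisfaction of about 61% (n = 30) or 63% (n = 35). Attrition could be reported as within its limit on data that do not exclude a true rate of about 39% or 37%. The verdict is unreliable when the true rate is within about 5 points of the cut-off, and fairly reliable at 65% or less or 90% or more. Session completion is probably less affected if pooled.

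This rests on patients being independent, on satisfaction being answered by all 30 or 35 (fewer respondents widen the interval), and on 35 being reached only if the user-testing patients are combined. It is an inexpensive improvement to make before analysis, not a flaw in the design.

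**What to change.** In the Analytic Plan for Aim 2, report:

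- retention (equivalently, attrition) and satisfaction, each with an exact 95% confidence interval;
- the denominator for each proportion, and for satisfaction how patients without a post-intervention questionnaire are counted;
- the share of sessions completed, with a 95% interval from a bootstrap that resamples patients, so that clustering of sessions is respected.

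In Treatment Feasibility and Acceptability, replace the sentence that equates 80% with demonstration. Suggested sense: the acceptability benchmark is met if the observed proportion is at least 80%, and the conclusion is stated together with the lower 95% confidence limit. Report retention and session completion in the same way, with the upper limit where attrition is the quantity reported.

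The benchmarks stay where they are, so the pass probabilities in the working do not change; what changes is that the conclusion carries its uncertainty. The cost is some plan wording and three intervals, with no new patients, data or design change. The downside is that the claim will look less definite.
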